3.4 Eligibility Criteria

Eligibility for participation in this study will be based on the inclusion/exclusion criteria. An individual subject may only be included in the study once.

Inclusion Criteria

- 1. Subject has documented Type 1 or Type 2 diabetes mellitus according to the ADA criteria (Appendix B).³³
- 2. Subject has daily pain attributed to symmetrical lower extremity diabetic peripheral neuropathy for at least 6 months prior to screening. Confirmed by score of ≥ 6 on the Toronto Clinical Neuropathy Scoring System.
- 3. Subjects' average lower extremity pain related to diabetic peripheral neuropathy over the preceding 24 hours is ≥4 and <9 based on the 11-point NPRS (0-10) at the Screening Visit.
- 4. Subject age is greater than or equal to 22 years and less than 80 years of age.
- 5. Subject is on stable diabetes treatment which should include medication and/or diet and exercise for at least 3 months prior to Screening.
- 6. Subject has an HbA1c $\leq 10\%$ at Screening or within 3 months of Screening.
- 7. Subject has not changed their analgesic prescriptions in the preceding one month.
- 8. Subject has an ankle-brachial index (ABI) of ≥ 0.8 to ≤ 1.3 . If the subject has incompressible vessels, a toe brachial index of 0.8 to 1.3 is required. These adequate lower extremity studies are with no documented intermittent claudication.
- 9. Subject walks independently with or without assistive devices, and does not require a wheel chair.
- 10. Subject is willing and able to give written informed consent and to comply with all parts of the study protocol.

- 11. Female subjects must be post-menopausal, surgically sterile, abstinent, or, if of childbearing potential, practicing (or agreeing to practice) an effective method of birth control if they are sexually active for the duration of the study. Effective methods of birth control include prescription hormonal contraceptives, intrauterine devices, doublebarrier methods, and/or male partner sterilization.
- 12. Subject can access an internet browser in the home environment or through a smart phone.

Enrollment Visit Inclusion Criteria

- 1. Average diabetic peripheral neuropathic pain intensity (NPRS score) is ≥ 4 and < 9 calculated as the mean of the daily NPRS scores for neuropathic pain in the lower extremities over the 7 days preceding the visit.
- 2. Subject has completed a minimum of 70% of the ePRO assessments during the run-in period.

Exclusion Criteria

- 1. Subject has an active, open ulcer on either lower extremity.
- 2. Subject has significant peripheral vascular disease defined as absence of more than one-foot pulse per foot and/or ABI <0.7 and >1.3 and/or history of angioplasty, peripheral bypass surgery, or claudication within 6 months of the Screening Visit.
- 3. Subject has venous insufficiency with an active ulcer as classified by the Venous Insufficiency Classification System of grade C6.
- 4. Subject has a history of previous solid organ transplant or severe renal disease (i.e. estimated creatinine clearance \leq 30 mL/min).
- 5. Subject has been diagnosed with a non-diabetic cause of chronic neuropathy (e.g. end stage renal disease, infectious etiology, chemotherapy, drug etiology, alcohol abuse, ingestion of toxic substance, nerve decompression surgery (related to lower extremity symptoms), or connective tissue disease) within the past 10 years.
- 6. Subject has previous or current history of primary or tertiary hyperparathyroidism, hypercalcemia, psychiatric disorder, alcohol dependency, Hepatitis B or C, or HIV infection.
- 7. According to the judgement of the Investigator, subject has clinically significant cardiovascular disease within 6 months prior to screening (unstable or poorly controlled

hypertension, transient ischemic attack, myocardial infarction, unstable angina, arrhythmia, cardiac surgery, stent placement or angioplasty, or congestive heart failure).

- 8. Subject has a history of any uncontrolled medical illness that, in the investigators judgment, places the subject at unacceptable risk for enrollment in a research trial with pulsed electromagnetic field therapy.
- 9. Subject requires or anticipates the need for surgery (other than minor day surgical procedures such as dental or minor cosmetic procedures not involving the lower extremities and not requiring extended use of analgesics) or extended travel during the treatment period.
- 10. Subject has a total foot depth (most inferior aspect of the medial malleolus to the plantar aspect of the foot when residing on a treatment pad) of >8 cm.
- 11. Subject has received any investigational drug or device within 30 days prior to the Screening Visit.
- 12. Subject has received long acting lidocaine, marcaine or bupivacaine injection products or other agents for nerve blocks within 6 weeks prior to the Screening Visit.
- 13. Subject has used chronic systemic corticosteroid treatment within 3 months of the Screening Visit.
- 14. Subject has a history of malignancy within the past 5 years in the treatment area.
- 15. Subject has severe mental health or psychiatric disorder of sufficient severity that would interfere with study performance and/or assessments, in the opinion of the Investigator.
- 16. Subject is receiving prn narcotic medications.
- 17. Subject has a known history of drug or alcohol abuse within one year prior to the Screening Visit.
- 18. Subject has an implanted pacemaker, defibrillator, neurostimulator, spinal cord stimulator, bone stimulator, cochlear implant, or other implanted device with an implanted metal lead(s).
- 19. Subject is currently pregnant or planning to become pregnant prior to Day 180.
- 20. Treatment of the lower extremity with PROVANT® Therapy System.
- 21. Subject is unwilling or unable to follow study instructions or comply with the treatment regimen, diary documentation, and study visits.
- 22. Subject has pain from any other source that can confuse the assessment of the pain associated with DPN.

- 23. Subject has a clinically significant foot deformity (Charcot Neuroarthropathy or Talipes Equinovarus).
- 24. Subject has been diagnosed with mononeuropathy in the lower extremities.
- 25. Subject has a skin condition that could alter their peripheral sensation (i.e. exfoliating skin conditions, dermatitis, bruises, weeping skin, skin lesions, infected skin, or necrotic skin) on the feet.
- 26. Subject has had previous surgery to the spine or lower extremity with residual symptoms of pain or difficulty with movement.
- 27. Subject has clinically significant arthropathy (i.e. rheumatoid arthritis, osteoarthritis, gout) that contributes to pain during casual walking or stair climbing.

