outcomes (WPAIQ and NeuroQoL), PGI, final measurements of SPP, NCS, QST and be assessed to determine their Toronto Clinical Neuropathy Score. Those subjects who consented and had biopsies collected at the Enrollment visit, will have their 4- month study biopsies during this visit and samples sent directly to the central laboratory for assessment. Subjects will return the study device and complete a blinding assessment.
Subjects that complete Part A will continue into the open-label extension period (Part B). All subjects will be reconsented if not completed at a prior visit and given an open-label active device. Subjects will record ePRO data for one week prior to the Month 6, 8, 10, and 12 visits following each morning treatment. Subjects will be reminded of the150-day (Month 5) phone call.
At Month 5 , subjects will receive a telephone call to ensure compliance to treatment, and to be assessed for safety and concomitant medication changes. Subjects will be reminded to record ePRO data for one week prior to the 180-day (Month 6) phone call.
At Month 6 , subjects will receive a telephone call to ensure treatment compliance and collection of diary data, and to assess safety and concomitant medication changes. Subjects will be reminded of the 210-day (Month 7) phone call.
At Month 7 , subjects will receive a telephone call to ensure treatment compliance, and to assess safety and concomitant medication changes. Subjects will be reminded to record ePRO data for one week prior to the 240-day (Month 8) visit.
At Month 8 , subjects will return to the clinic for evaluation of safety, measure QST, treatment satisfaction, review of device usage (reports will be supplied to the site) and collection of diary data, concomitant medication changes, quality of life outcomes (NeuroQoL), and PGI. Subjects will be reminded of the 270-day (Month 9) phone call.
At Month 9 , subjects will receive a telephone call to ensure treatment compliance, and to assess safety and concomitant medication changes. Subjects will be reminded to record ePRO data for one week prior to the 300-day (Month 10) phone call.

	At Month 10 , subjects will receive a telephone call to ensure treatment compliance and collection of diary data, and to assess safety and concomitant medication changes. Subjects will be reminded to record ePRO data for one week prior to the 330-day (Month 11) phone call.

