3.5 Enrollment

Subjects are considered enrolled in this study when all the following have occurred:

- 1. Written informed consent is obtained
- 2. All inclusion criteria and no exclusion criteria have been met
- 3. All screening evaluations are complete as outlined in section 4.1

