4.1 Visit 1 – Screening Visit (Day -15)

The Screening Visit will take place 15 days prior to the Enrollment Visit. If a successfully screened subject falls more than 1 day early (earlier than day -14) or more than 2 days late (later than day -17), the subject will require another screening and run-in period to

participate in the trial. The following procedures will be performed during the Screening Visit:

- 1. Informed consent review and signature
- 2. Review Inclusion and Exclusion criteria
- 3. Collect Toronto Clinical Neuropathy Scoring System for Inclusion
- 4. Obtain baseline pain score (baseline score must be \geq 4 and <9 for eligibility)
- 5. Collect subject demographic data (including age, weight, height, gender, race/ethnicity)
- 6. Collect baseline diabetes related health resource utilization including the regimen for their diabetic care (number of doctors' visits and history of ulcers)
- 7. Collect Medical and Surgical History
- 8. Collect depth, width, and length foot measurements and shoe size for each foot
- 9. Conduct directed physical exam (abnormal or normal) for General Appearance, Cardiovascular, Musculoskeletal, Extremities/Skin, Neurological, and Other
- 10. Obtain Ankle-Brachial Index
- 11. Assess venous insufficiency
- 12. Measure HbA1c
- 13. Review and record medications taken for their diabetic neuropathy pain (including over the counter PRN)
- 14. Review and record all additional medications
- 15. Perform a urine pregnancy test for females of child bearing potential
- 16. If the subject meets the eligibility criteria, enroll the subject in to the 14-day ePRO run in period in the ePRO system.

During this visit, the subject will be introduced to the electronic (ePRO) diary and trained in the proper use of the patient-reported-outcome (PRO) assessment tools for pain intensity and analgesic consumption for their diabetic neuropathy pain (including over the counter and prn medications). Analgesic medications taken for their diabetic neuropathy pain will be captured in the ePRO and subjects will enter the number of pills they have taken over the last 24 hours. The ePRO diary can be accessed by the subject through any device that has an internet connection and web browser.

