4.3 Visit 2 – Enrollment Visit (Day 0)

The following procedures will be performed:

- 1. Review Inclusion/Exclusion criteria
- 2. Review and record any changes in medical history and study eligibility criteria since screening.
- Review average baseline NPRS score collected in ePRO (mean of the preceding 7 days must be ≥4 and <9).
- 4. Review diary compliance (must be \geq 70%)
- 5. Review analgesic pain consumption profile in ePRO
- 6. Review and record adverse events since signing of the Informed Consent
- 7. Review and record any changes in concomitant medications
- 8. Conduct Skin Perfusion Pressure (SPP)
- 9. Conduct Sural Nerve Conduction Studies (NCS)
- 10. Conduct Quantitative Sensory Testing (QST) of Cool, Warm, and Heat as Pain
- 11. Collect WPAIQ
- 12. Collect NeuroQoL
- 13. Collect Biopsies at distal thigh and distal leg from consenting subjects
- 14. If the subject continues to meet eligibility criteria, enroll and randomize subject
- 15. Introduce and train the subject on the use of the PROVANT[®] Therapy System, including instructions for proper positioning and operation of the devices.

- 16. Remind the subject in the use of patient-reported-outcome (PRO) tools of NPRS and analgesic consumption for their diabetic neuropathic pain.
- 17. Enroll the subject into the treatment period in the ePRO system.

During this visit, eligible subjects will receive a randomized Provant device and will be instructed to administer treatment on both feet twice daily at 8am and 8pm (\pm 2 hours) for 4 months (120 days).

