- 13. Collect Toronto Clinical Neuropathy Scoring System
- 14. Conduct Blinding Assessment
- 15. Assess adherence to PEMF treatment regimen by reviewing the usage report provided by Regenesis Biomedical and ePRO entries
- 16. Return of randomized device
- 17. Enroll Subject in Part B / open-label part of protocol

During this visit, subjects will receive an Active Provant device and will be instructed to administer treatment on both feet twice daily at 8am and 8pm (\pm 2 hours) for 8 months (through Day 360).

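### Exclusion 19 stops at Day 180 although active treatment runs to Day 360; the contraception criterion leaves only a narrow gap, so this is a minor wording fix

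*Protocol*

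**What the plan says.** Two entry criteria in Protocol section 3.4 deal with pregnancy.

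- Exclusion 19, repeated in the synopsis: "Subject is currently pregnant or planning to become pregnant prior to Day 180".
- Inclusion 11 admits women who are post-menopausal, surgically sterile or abstinent. It also admits women of childbearing potential who are "practicing (or agreeing to practice) an effective method of birth control if they are sexually active for the duration of the study".

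Both apply to every subject. Section 3.5 makes enrollment conditional on "All inclusion criteria and no exclusion criteria have been met", and the Day 0 visit in section 4.3 again lists "Review Inclusion/Exclusion criteria".

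On exposure, section 4.8 gives Part A completers an active device at Month 4, to be used twice daily "for 8 months (through Day 360"). The synopsis says of Part B entry: "All subjects will be reconsented if not completed at a prior visit and given an open-label active device".

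On testing, section 4.1 lists "Perform a urine pregnancy test for females of child bearing potential" at Screening. The schedule in Appendix A shows no later test.

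**The concern.** Day 180 marks the end of neither part of the study. Part A treatment ends on Day 120 and Part B treatment on Day 360. In the schedule, Day 180 is only the Month 6 telephone call. An eligibility date that is meant to keep pregnancy and device exposure apart should follow the exposure period, and this one stops halfway through it.

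The practical risk is that sites receive two time limits for one precaution. A coordinator who looks only at Exclusion 19 could conclude that a pregnancy planned for, say, Day 200 is no obstacle, although the woman would be on an active device at that point. Entry wording carries more weight here than usual because the protocol has no pregnancy-specific control after Screening other than these two criteria.

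**Working it through.** **1. Exposure period.** Part A treatment is Days 1 to 120, which is 120 days (sections 3.7.1 and 3.10). Part B is Days 121 to 360: 360 − 120 = 240 days. These agree with the full-adherence counts of 120 and 240 in section 4.17.

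**2. Exclusion 19 taken alone.** The last day before Day 180 is Day 179, so the days not covered are 180 to 360.
- Number: 360 − 180 + 1 = 181 days.
- Share of all device days: 181 / 360 = 50.3%.
- Share of Part B: 181 / 240 = 75.4%.
- Part A days not covered: 0. Cover runs 179 − 120 = 59 days past the end of Part A treatment.

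**3. Both criteria together, for a woman of childbearing potential planning pregnancy between Day 180 and Day 360.**

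| Situation at entry | Inclusion 11 | Exclusion 19 | Result |
|---|---|---|---|
| Sexually active | Must agree to contraception for the whole study, which she cannot do truthfully | Not triggered | Not eligible |
| Abstinent | Met: abstinence is a category of its own with no stated duration | Not triggered | Meets the letter of both |

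The wording has a second, smaller looseness. In Inclusion 11 the closing time phrase can attach to being sexually active instead of to the use of birth control. The SAP (section 4.4) puts a subject's time on study at about 12 months, so on the natural reading the contraception requirement spans all of Part B.

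**4. Later controls.** Scheduled contacts after randomization are Days 7, 30, 60, 90, 121, 150, 180, 210, 240, 270, 300, 330 and 361, which is 13. The procedure lists in sections 4.4 to 4.16 contain no pregnancy item at any of them. General routes do exist. Adverse events and concomitant medications are assessed at every contact, section 5 allows withdrawal in the subject's best medical interest, and section 11.1 counts a birth defect as a serious adverse event.

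**5. Number affected.** The documents do not give the number of women of childbearing potential. The following shares are assumptions, for illustration only: 5 to 15% of 170 subjects are such women, 10 to 30% of them qualify only as abstinent, and 1 to 5% of those plan pregnancy between Day 180 and Day 360.
- Low: 170 × 0.05 × 0.10 × 0.01 = 0.0085.
- High: 170 × 0.15 × 0.30 × 0.05 = 0.38.

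Fewer than one woman is expected across the whole range.

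**The case against.** The strongest reply is that the matter is already handled. No one is screened on Exclusion 19 alone. Inclusion 11 covers sexually active women throughout, Inclusion 10 requires willingness to comply with the whole protocol, and Exclusion 21 removes anyone unwilling to follow study instructions. In ordinary reading, a woman who intends to conceive in Part B is not abstinent in the sense intended. This stands for almost every case. It does not supply the missing duration for abstinence, and it does not explain Day 180.

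It can also be said that no harm is shown. The anticipated device effects in section 11.2 are local to the application area, and section 6 judges the device to pose no serious risk. This stands too, and it is why the point is precautionary. The consent form and the device instruction manual were not available for this check and may carry further precautions.

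A reader might infer three stronger things that the documents do not support.

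- *Half of the device period is unprotected.* The 181 days describe Exclusion 19 in isolation. Inclusion 11 covers the same days for sexually active women.
- *The two criteria contradict each other.* They do not. Both must be satisfied, so the stricter one governs.
- *Neighbouring criteria follow full exposure and Exclusion 19 is the odd one out.* Exclusion 9 bars "extended travel during the treatment period", but sections 3.12.1 and 3.12.2 use that term for the 120 days of Part A. It is therefore no evidence of a limit running to Day 360.

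**Conclusion.** The date mismatch is real and unexplained, and it appears in both places where the criterion is stated. Its practical reach is small: a woman abstinent at entry, planning pregnancy after Day 180, at a site that reads Inclusion 11 literally. The expected number is below one, on shares that are assumed and not taken from the documents. The randomized comparison, the error rate and the sample size are untouched, because Part A lies wholly within the period that Exclusion 19 covers.

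A reader might also infer that Day 180 is left over from a shorter design, since section 4.1 bars new analgesics through Day 180 while section 4.19 bars changes through Day 360. That fits, but the documents do not say so, and the conclusion does not depend on it.

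The rating is minor. The case for acting is that the correction costs little and the documents show no benefit from keeping Day 180.

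**What to change.** At the next amendment:

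- **Exclusion 19, section 3.4 and synopsis.** Replace the Day 180 limit with the end of the study, so that a woman is excluded if she is pregnant at entry or plans a pregnancy *during the study (through Day 361)*.
- **Inclusion 11, section 3.4, and the synopsis wherever it is repeated.** Keep the post-menopausal and surgically sterile categories. For all other women, require agreement *either to remain abstinent or to use an effective method of birth control for the duration of the study (through Day 361)*. This gives abstinence a duration and removes the ambiguity in the time phrase.
- **Consent text.** Match it to the new wording. The re-consent already planned at Part B entry is enough for women in Part A. A separate re-consent round is not called for: section 8 ties re-consent to new safety information, which this is not, and enrolled sexually active women of childbearing potential are already bound by Inclusion 11.

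The cost is a wording amendment with IRB review, at up to 20 sites, and possibly a very few more screen failures. No visit or test is added. Afterwards both criteria give the same limit, and Exclusion 19 leaves no device day uncovered.

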3.5 Enrollment

Subjects are considered enrolled in this study when all the following have occurred:

- 1. Written informed consent is obtained
- 2. All inclusion criteria and no exclusion criteria have been met
- 3. All screening evaluations are complete as outlined in section 4.1

3.6 Randomization

The schedule for randomization of subjects and allocation to treatment will be prepared using SAS[®] (Statistical Analysis System; Cary, NC) to create a computer-generated scheme based on a permuted block algorithm. Randomization will be stratified by each site. The randomization schedule will randomize in a 1:1 ratio (42 μ s : sham) to a device based on the randomization kit numbers. The kit numbers will be assigned sequentially to subjects that qualify for inclusion into the study.

3.7 Device Description

The Provant[®] Therapy System is a solid-state, fixed-power output radio frequency generator and transmitter designed to operate at the Federal Communication Commission (FCC) authorized medical device frequency of 27.12 MHz. The primary components are the control unit, the treatment applicator(s) that generate and deliver the shortwave RF energy. Key functions and features of these components are as follows:

3.7.1 Control Unit

The control unit contains the main electronics, software, and user interface of the system. The control panel (Figure below) has an LCD display which is located on the front of the control panel with an indicator light above the display and buttons to either side of

the LCD screen. The indicator light changes color to inform the patient along with the LCD verbiage. The five (5) buttons are located to the right and left sides of the LCD (2 on the left, 3 on the right) and light up when needed. The top left button serves as a power on/off switch and bottom left serves as a start/stop therapy switch. The top right button serves as a pause/resume therapy during treatment. The middle right and bottom right buttons are for future use and will be not be active.

When the system is plugged in, the Provant Therapy System enters a "soft power" mode, waiting for the user to press the power on/off button. Once the power on/off button is depressed, the system enters an active mode, performs some internal diagnostics to assure functionality, then proceeds to inform the patient to place the midfoot of each foot over each treatment applicator and press the start button to initiate therapy.

Pressing the start button initiates a preset, thirty (30)-minute therapy session and treatment sequence described in greater detail below. Once therapy is initiated, the LCD screen will indicate the remaining time as well as the number of minutes completed. Pressing either the power on/off button, the therapy start/stop button or the therapy pause/resume button after a therapy session has started will stop the RF energy generation. The power on/off button will initiate a power down of the system. The therapy start/stop button will initiate termination of the current therapy session. The therapy pause/resume button will allow for pausing and continuation of a therapy session. All buttons have a tactile resistance and emit a small chirp when pressed.

When the thirty-minute therapy session is concluded, the generation of RF energy is automatically terminated and an audible tone is generated to alert the user that the treatment is finished. The LCD screen then instructs the user to press the power on/off button to power down the system. The patient can either store the unit or leave plugged in until the next use.

RBI.2017.002 Version C

The Provant[®] Therapy system also has additional functions, independent of the user interface. The system logs internally any errors encountered, start and stop times of treatment, as well as feedback from the treatment applicator at predefined intervals. This data is stored on an internally mounted SD card (no external access) and the data can be read upon return of the device or can also be relayed back to the Sponsor's engineering technicians through the device's cellular module.

In this study, the subject will treat both feet for 30 minutes, twice a day for 120 days. Subjects will be instructed to treat barefooted, placing each bare foot on a treatment applicator and treating for the full 30 minutes, twice a day.

